Appendix 2 Schedule of Study Procedures – GTI1401-OLE

Procedures/Assessments	Visits	Screening/Ext Week 1 Visit		Weekly On-Site Infusion Visits (Ext Weeks 2 to 52)	Quarterly Visits (Ext Weeks 12, 24, 36, 48)	Bi-Annual Visits		End of Study Follow-Up Assessment ^b (via phone call) (Ext Week 53)
		Screening ^a	Initiation of Infusion			Ext Week 26	Ext Week 52	
Informed consent		X					X	
Inclusion/exclusion criteria		X						
Subject number confirmed		X						
Weight					X			
Collection of virus safety retain samples							X	
Physical exam (excludes breast and genitourinary)						X	X	
Urine pregnancy test (potential child-bearing females only)						X	X	
Urine cotinine						X	X	
Blood for hematology and chemistry laboratory assessments						X	X	
Blood for retains for possible future testing						X	X	
Urinalysis						X	X	
Vital signs (heart rate, blood pressure, respiratory rate, and temperature)			X	X	X	X	X	
Pre- and post-bronchodilator PFTs (FEV ₁ and FVC)						X	X	
Blood for Alpha ₁ -PI level					X			
Alpha-1 MP IV infusion			X	X	X	X	X	
COPD exacerbation assessment						X	X	X
Adverse event assessment				X	X	X	X	X
Concomitant medications assessment				X	X	X	X	X

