3.1 Primary Objectives

The primary objective of GTI1401 study is to evaluate the safety of 60 mg/kg Alpha-1 MP administered by weekly IV infusions over eight weeks in Japanese subjects with AATD.

The primary objective of GTI1401-OLE study is to evaluate the long-term safety of 60 mg/kg Alpha-1 MP administered by weekly IV infusions for approximately one year or longer (can be renewed annually with the consent of the subjects) in adult subjects with AATD in Japan.

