11.1 Adverse Events

Definition of Adverse Events

Adverse Event:
	
An AE is any untoward medical occurrence in a subject or clinical investigation subject administered a pharmaceutical product, which does not necessarily have a causal relationship with this treatment.
 
An AE can therefore be any unfavorable and unintended sign (including an abnormal laboratory finding), symptom, or disease temporally associated with the use of a medicinal product, whether or not considered related to the IMP.
 
In this protocol, non-serious COPD exacerbation will not be considered as adverse events unless SAE.

TEAE for GTI 1401
	
Treatment emergent adverse events (TEAE) for GTI 1401 will defined as any adverse event occurred after or on the first study drug infusion of GTI 1401 to the final visit of GTI 1401.
 
For any subject, all AEs that occur at any time from the beginning of Alpha-1 MP administration until the final visit of the clinical trial will be considered as TEAE.
 
All tables regarding to Adverse Events are restricted to TEAE.

TEAE for GTI1401-OLE
	
Treatment emergent adverse events (TEAE) for GTI 1401-OLE will defined as any adverse event occurred after or on the first study drug infusion of GTI 1401-OLE to the final visit of GTI 1401-OLE or adverse event which continue from GTI 1401 to GTI 1401-OLE.
 
For any subject, all AEs that occur at any time from the beginning of Alpha-1 MP administration until the final visit of the clinical trial will be considered as TEAEs
 
All tables regarding to Adverse Events are restricted to TEAE.

Adverse Drug Reaction (ADR):
	
The phrase “responses to a medicinal product” means that a causal relationship between a medicinal product or study treatment and an AE is at least a reasonable possibility, that is, the relationship cannot be ruled out.

	
When an AE is classified, assessing causal relationship by the Investigator, as “definitive”, “probable”, “possible” or “doubtful/unlikely”, the event will be defined as a suspected ADR. When the causal relationship is labeled “Unrelated”, then it will be considered that the AE is not imputable to the study treatment and it is not a suspected ADR.

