
Serious Adverse Events (SAEs):
	
Any event reported on the AE CRF form with the serious field ticked “Yes”.
 
A SAE is any untoward medical occurrence that at any dose:
 
Results in death
 
Is life-threatening
 
Note: The term “life-threatening” in this definition refers to an event in which the subject is at risk of death at the time of the event; it does not refer to an event that hypothetically might cause death if it were more severe.
 
Requires inpatient hospitalization or prolongation of existing hospitalization
 
Results in persistent or significant disability/incapacity
 
Is a congenital anomaly/birth defect

Events of Special Interest :
	
Events of special interest include the following:
 
All COPD exacerbations occurring during the study will be recorded. Each subject will be assessed for signs and symptoms of exacerbations at each study visit as specified in Appendix 1 and Appendix 2. Given that COPD exacerbations are part of the natural history of AATD, COPD exacerbations will not be reported as AEs unless a COPD exacerbation meets the criteria of a SAE. If an exacerbation meets criteria for a SAE, it will be reported as such, and the standard of care should be followed. Results from standard of care should be obtained and reported.

Adverse events with incomplete start dates will be considered treatment emergent (TEAE) if:

- Day and Month are missing and the year is equal to or after the year of the first study drug dose date of each study (1401/1401-OLE);

- Day is missing, month is present and the month is equal or after the month of first dose of each study (1401/1401-OLE) and the year is equal or after the year of first dose date of each study (1401/1401-OLE);
- Day is missing and the year is equal to the year of the first infusion date of each study (1401/1401-OLE) and the month is equal to or after the month of the first infusion date of each study (1401/1401-OLE);
- Complete date is missing.

The AE tables will include the number and percentage of subjects by MedDRA primary System Organ Classes (SOC) - sorted by alphabetical order, MedDRA Preferred Terms (PT) - sorted by alphabetical order. A subject with more than one occurrence of the same adverse event in a particular system organ class/preferred term will be counted only once in the total of those experiencing adverse events in that particular system organ class/preferred term.

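### The extension schedule marks COPD exacerbation assessment only at Ext Weeks 26, 52 and 53, although subjects attend weekly, so non-serious exacerbations may be less completely and less accurately ascertained than in GTI1401

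*SAP*

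**What the plan says.** SAP 3.1 gives the purpose of the extension: "The primary objective of GTI1401-OLE study is to evaluate the long-term safety of 60 mg/kg Alpha-1 MP". SAP 4.2 lists COPD exacerbations as a variable for both studies.

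SAP 11.1 makes exacerbations the only event of special interest. It states: "All COPD exacerbations occurring during the study will be recorded". On timing it says: "Each subject will be assessed for signs and symptoms of exacerbations at each study visit as specified in Appendix 1 and Appendix 2". The adverse event definition in the same section adds that "non-serious COPD exacerbation will not be considered as adverse events unless SAE".

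SAP Appendix 2 has a column headed "Weekly On-Site Infusion Visits (Ext Weeks 2 to 52", followed by columns for the quarterly visits (Ext Weeks 12, 24, 36 and 48), Ext Week 26, Ext Week 52 and the Ext Week 53 call. The rows "Adverse event assessment" and "Concomitant medications assessment" are marked in all of these columns. The row "COPD exacerbation assessment" is marked only in the last three.

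In GTI1401 (SAP Appendix 1 and Protocol Appendix 1) exacerbations are evaluated at every visit.

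**The concern.** A non-serious exacerbation is outside the adverse event record by rule, so the dedicated assessment is its main route into the data. In the extension that assessment comes about twice a year. Take an exacerbation that starts in Ext Week 4 and is managed at home: its first scheduled enquiry is at Ext Week 26, 22 weeks later. The layout plan's listing of non-serious COPD exacerbations asks for start and end date and time, severity, dyspnea, cough, sputum and its colour, and changes in treatment. Such details are hard to reconstruct after months.

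The affected outputs are the event-of-special-interest counts in the adverse event overview (SAP 11.1.1) and that listing, in a study whose primary objective is long-term safety. The overview would place adverse events asked about weekly beside exacerbations asked about half-yearly, with no note of the difference.

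**Working it through.** The plan states no figure on this point, so the check is a count of schedule marks and the gaps between them.

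**Inputs.** Extension contacts run weekly from Ext Week 1 to Ext Week 53: 52 on site and one by phone (SAP Appendix 2). Ext Week 1 is the same visit as GTI1401 Week 9 (SAP 4.1), where exacerbations are evaluated (SAP Appendix 1), so the clock starts there.

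| | GTI1401, Screening to Week 9 | Extension, Ext Weeks 2 to 53 |
|---|---|---|
| Exacerbation assessments marked | 13 (Screening, Weeks 1 to 8, PK1, PK2, PK5, Week 9) | 3 (Ext Weeks 26, 52, 53) |
| Longest scheduled gap on treatment | about 1 week | 26 weeks |
| Adverse event and medication review | every visit | every weekly and quarterly visit, and Ext Weeks 26, 52 and 53 |

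**Gaps in the extension.** 26 − 1 = 25 weeks; 52 − 26 = 26 weeks; 53 − 52 = 1 week.

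**Share of contacts with the assessment.** 3/53 = 5.7%; on site only, 2/52 = 3.8%.

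**Mean delay from week of onset to the next assessment**, with onset equally likely in each of the 52 weeks after Ext Week 1: [(0 + 1 + … + 24) + (0 + 1 + … + 25) + 0]/52 = (300 + 325 + 0)/52 = 12.0 weeks.

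**How much could be lost.** The documents give no exacerbation rate and no measure of recall, so this cannot be estimated. As an illustration only, assume that the dedicated assessment is the sole source and that an event stays reportable from one week to the next with probability r. The share counted is then [Σ r^k for k = 0 to 24, plus Σ r^k for k = 0 to 25, plus 1]/52:

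| Assumed r | 1.00 | 0.99 | 0.98 | 0.95 | 0.90 |
|---|---|---|---|---|---|
| Share counted | 100% | 89% | 79% | 58% | 38% |

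On the same model weekly assessment gives 100% throughout. The range mainly shows that the answer depends on an unknown input.

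**The passages side by side.** The SAP 11.1 sentence on timing names each study visit and then defers to the two appendices. Appendix 1 satisfies it on any reading. Appendix 2 satisfies it only if the reference limits the phrase to the marked visits. On that reading the timing conflict largely goes, but the undertaking to record every exacerbation has no stated mechanism between Ext Weeks 1, 26 and 52.

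**The case against.** The strongest reply is that a sparse dedicated assessment need not mean sparse capture.

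- SAP 11.1 undertakes to record every exacerbation, not only those elicited at marked visits.
- Adverse events are reviewed weekly. If the extension follows the core protocol, the prompt is an open question about any change since the last visit (Protocol 5.3.7), which could bring out new respiratory symptoms.
- Medication is also reviewed weekly, including dose and frequency (Protocol 4.5). Mild exacerbations are defined by more of the usual medication and moderate ones by systemic steroids or antibiotics (Protocol 4.6.1), so either may leave a trace there.
- Severe exacerbations are defined by hospitalization, which is an SAE criterion (Protocol 5.3.6).
- The extension protocol is not among the documents and the text of Appendix 2 footnotes a and b is not shown, so further visit instructions cannot be excluded.

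Most of this stands. A reader might infer that the extension under-counts exacerbations, or that they rest wholly on recall; the documents show only a risk. A reader might also expect a lower extension rate to be taken for long-term benefit, but SAP section 5 presents the two studies separately and no between-study comparison of exacerbations is planned.

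The reply does not close the gap. The documents give no instruction to move an event noticed during weekly adverse event or medication review onto the exacerbation record. A medication entry alone does not supply symptoms or severity. Mild events, which subjects control themselves, are the most exposed.

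**Conclusion.** The point holds as a weakness in scheduled ascertainment, together with wording that needs reconciling. Scheduled exacerbation assessments in the extension are up to 26 weeks apart, against about 1 week on treatment in GTI1401, for the only event of special interest. Non-serious events, especially mild ones, may be less completely counted and less accurately dated and graded. The size is unknown and may be zero.

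This rests on Appendix 2 as printed being the operative schedule and on the extension protocol adding no instruction for capture between marked visits. It is not a flat contradiction, because the cross-reference in SAP 11.1 allows a reading under which the texts agree on timing. The change is worth making because it is cheap and improves a planned safety output.

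**What to change.** Mark the COPD exacerbation assessment at the weekly and quarterly visits in SAP Appendix 2 and in the matching extension schedule, next to the adverse event and medication rows already marked there. The longest interval falls from 26 weeks to 1, and SAP 11.1 and Appendix 2 then agree.

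The layout plan is dated 21 March 2017, so the extension may already be running. If its schedule can no longer change, reword SAP 11.1 to name the visits at which exacerbations are actually assessed, and state the assessment interval beside the extension's exacerbation counts and listing.

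The cost is a schedule amendment with its approvals and a few minutes of CRF work per visit. If the extension follows the core protocol's amendment rule (Protocol 10.1 and 10.3), approval is needed at each study center; about 5 institutions were planned for GTI1401 (Protocol 4.1.1). No new visit, sample or staff is needed. The fallback costs only text.

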Appendix for Laboratory Parameter:

Display order	Category for Lab Test	LB parameter code	LB parameters (SI unit)	Digit to be displayed
1	HEMATOLOG Y	HGB	Hemoglobin [g/L]	Integer
2	HEMATOLOG Y	HCT	Hematocrit [%]	1 decimal place
3	HEMATOLOG Y	PLAT	Platelets [$10^9/L$]	Integer
4	HEMATOLOG Y	RBCH	Erythrocytes [$10^{12}/L$]	2 decimal place
5	HEMATOLOG Y	WBCH	Leukocytes [$10^9/L$]	1 decimal place
6	HEMATOLOG Y	NEUT	Neutrophils [%]	Integer
7	HEMATOLOG Y	LYM	Lymphocytes [%]	1 decimal place
8	HEMATOLOG Y	MONO	Monocytes [%]	1 decimal place
9	HEMATOLOG Y	EOS	Eosinophils [%]	1 decimal place
10	HEMATOLOG Y	BASO	Basophils [%]	1 decimal place
11	CHEMISTRY	SODIUM	Sodium [mmol/L]	Integer
12	CHEMISTRY	K	Potassium [mmol/L]	1 decimal place
13	CHEMISTRY	CREAT	Creatinine [mg/dL]	2 decimal place
14	CHEMISTRY	CA	Calcium [mg/dL]	1 decimal place
15	CHEMISTRY	UREAN	Urea Nitrogen [mg/dL]	Integer
16	CHEMISTRY	BICARB	Bicarbonate [mmol/L]	1 decimal place
17	CHEMISTRY	ALB	Albumin [g/L]	Integer
18	CHEMISTRY	AST	Aspartate Aminotransferase [IU/L]	Integer
19	CHEMISTRY	ALT	Alanine Aminotransferase [IU/L]	Integer
20	CHEMISTRY	ALP	Alkaline Phosphatase [IU/L]	Integer
21	CHEMISTRY	GLUCC	Glucose [mg/dL]	Integer
22	CHEMISTRY	PROTC	Protein [g/L]	Integer
23	CHEMISTRY	BILI	Bilirubin [mg/dL]	1 decimal place
24	URINALYSIS	PH	pH	
25	URINALYSIS	PROT	Protein	
26	URINALYSIS	GLUC	Glucose	
27	URINALYSIS	OCCBLD	Occult Blood	
28	URINALYSIS	MUCTH R	Mucous Threads	

Layout Plan

GTI1401

Protocol title: A Multi-Center, Open-Label Study to Evaluate the Safety and Pharmacokinetics of Weekly Intravenous Infusions of Alpha1-Proteinase Inhibitor (Human) in Japanese Subjects with

GTI1401-OLE

Protocol title: A Multi-Center, Open-Label Study to Evaluate the Long-term Safety of Weekly Intravenous Infusions of Alpha1-Proteinase Inhibitor (Human) in Japanese Subjects with Alpha1 Antitrypsin Deficiency

Study code: Alpha-1 MP

Sponsor: Grifols Therapeutics Inc.
[name]

LP status: V1.0

Date: 21MAR2017

Approval:

MAR 21, 2017

Date

Mar 21, 2017

Date

MAR 01, 2017

Date

Mar 23, 2017

PhD

Pharm.D.

MD

Date

Change Record

Version No.	Date	Author	Description of changes (revisions and reasons)
V0.1	2016/5/25	[REDACTED]	Created 1st draft
V0.2	2016/12/2	[REDACTED]	Incorporated client's review of 1st draft
V0.3	2016/3/1	[REDACTED]	Incorporated client's review of 2nd draft and MW input
V1.0	2016/3/21	[REDACTED]	Removed review comment

No	ID of TFLs	Title of TFLs	Statistical Analysis Plan	Number of Table	GTI1401	GTI1401-OLE	Remarks
1	Disp-1	6.1 Summary Table of Analysis Population		6	Subject Disposition		
2	Disp-2	6.2 Summary Table of Subjects Who Discontinue From the Study					
3	Disp-L1	6.3 Listing of Subject Disposition					"6.4 Listing of Screening Failures" will be based on this table layout.
4	Devi-1	7.1 Summary Table of Protocol Deviations		7	Protocol Deviations		
5	Devi-L1	7.2 Listing of Protocol Deviation					
6	Demog-1	8.1 Summary Table of Demographics		8	Demographics		
7	Demog-L1	8.2 Listing of Demographic Characteristics					
6	Demog-L2	8.3 Listing of Smoking History					
7	Demog-L3	8.4 Listing of Medical History					
8	Con-1	9.1.1 Summary Table of Prior Medication		9	Treatments and Medications	9.1 Prior and Concomitant Medication	"9.1.2 Summary Table of Concomitant Medication" will be based on this table layout
9	Con-L1	9.1.3 Listing of Medications					
10	Exp-1	9.2.1 Summary Table of Drug Exposure				9.2 Extent of Exposure	
11	Exp-2	9.2.2 Summary Table of Infusion Interruptions					
12	Exp-L1	9.2.3 Listing of Exposure Information					
13	Comp-1	9.3.1 Summary Table of Treatment Compliance				9.3 Treatment Compliance	
14	Comp-L1	9.3.2 Listing of Treatment Compliance					
15	Pk-1	10.1.1 Summary Table of Alpha-1-PI Concentrations	10 Exploratory Analysis	10.1	PK Analysis (GTI1401 only)		
16	Pk-2	10.1.2 Summary Table of Trough (pre-infusion) Levels (Cmin) and mean Cmi					
17	Pk-3	10.1.3 Figures of Concentration Versus Time Curves of Individual Subjects					
18	Pk-4	10.1.4 Figures of Concentration Versus Time Curves of All Subjects					
19	Pk-5	10.1.5 Summary of PK Parameters					
20	Pk-L1	10.1.6 Listing of Alpha-1-PI Concentrations (Week 8 and 9)					
21	Pk-L2	10.1.7 Listing of Alpha-1-PI Concentrations					
22	Pk-L3	10.1.8 Listing of Trough (pre-infusion) levels (Cmin) and mean Cmin					
23	Pk-L4	10.1.9 Listing of PK Parameters					
24	Mo-1	10.2.1 Summary Table of Lung Density					
25	Mo-L1	10.2.2 Listing of Lung Density					
26	AE-1	11.1.1 Overview of AEs	11 Safety Analysis	11.1	Adverse Events		
27	AE-2	11.1.2 Summary Table of AEs					"11.1.3 Summary Table of ADRs" will be based on this table layout.
28	AE-3	11.1.4 Summary Table of AEs by Causality					
29	AE-4	11.1.5 Summary Table of AEs by Severity					"11.1.6 Summary Table of ADRs by Severity" will be based on this table layout.
30	AE-L1	11.1.7 Listing of AEs					"11.1.10 Listing of AEs leading to Premature Discontinuation from the Study" will be based on this table layout.
31	AE-L2	11.1.8 Listing of Death					
32	AE-L3	11.1.9 Listing of SAE					
33	AE-L4	11.1.11 Listing of Non-Serious COPD Exacerbation					
34	Lb-1	11.2.1 Summary Table of Laboratory Test		11.2	Laboratory Tests		Tables for all the laboratory examination item described on SAP will be based on this table layout
35	Lb-2	11.2.2 Summary Shift Table of Laboratory Test (Low, Normal and High)					Chemistry and hematology laboratory parameter described on SAP will be based on this table layout.
36	Lb-3	11.2.3 Summary Shift Table of Laboratory Test (Normal and Abnormal)					Urine laboratory parameter described on SAP will be based on this table layout.
37	Lb-L1	11.2.3 Listing of Laboratory Parameters					
38	Vs-1	11.3.1 Summary Table of Vital Signs		11.3	Vital Signs		
39	Vs-L1	11.3.2 Listing of Vital Signs					
40	Ecg-1	11.4.1 Summary Table of Electrocardiogram		11.4	Electrocardiogram		
41	Ecg-L1	11.4.2 Listing of Electrocardiogram					
42	Ur-1	11.5.1 Summary Table of Urine Cotinine Test		11.5	Urine Cotinine Test		
43	Ur-L1	11.5.2 Listing of Urine Cotinine Test					
44	Pul-1	11.6.1 Summary Table of Pulmonary Function Tests (FEV1 and FVC)		11.6	Pulmonary Function Tests		
45	Pul-2	11.6.2 Summary Table of Pulmonary Function Tests (FEV1 % Predicted)					
46	Pul-L1	11.6.3 Listing of Pulmonary Function Tests					
47	Pr-L1	11.7 Listing for Pregnancy Tests		11.7	Pregnancy Test		
48	CT-L1	11.8 Listing for CT Scan		11.8	CT Scan		
49	PE-L1	11.9 Listing for Physical Examination		11.9	Physical Examination		

General Setting

Items	Contents
Paper Size	
 - A4 * The documents should allow printing in A4 without changing the page setup of the documents. * Landscape orientation is preferred, portrait is allowed.
Margin	
 - top, bottom, left, and right: 2.54 cm (1 in)
Font type and size	
 - Times New Roman 9pt or larger for all * For tables, when space is an issue (i.e. in terms of the page setup), the following solutions can be used (in the following order shown below): 
 - stacking, abbreviation; - split tables across pages; - split listings into sections.
Display	
 - For tables, when there is no subject to be counted, '0' will be displayed. - In the case of percentage or summary statistics can not be calculated (e.g. Denominator is 0 or there is no denominator), '-' will be displayed. If no subject to be counted and Denominator >0 then display "0" instead of "0 (0.0)".
Alignment	
 - The output should be left aligned on the page. - Titles and footnotes should be left aligned. - Column headers and column contents for text variables should be left justified, while column headers and column content for numeric variables should be centered. Concatenation of statistics, counts and percentages should be centered. - For variables displayed as numerical output (including dates and concatenation of statistics), and which have the same data format on all rows, the data should be aligned on the decimal point and be centered within the column.
Other	
 - The setting defined above in general is applicable unless otherwise specified. - A unit “μ” will be presented as “u” in tables and listings. - A unit ”temperature degree” will be presented as “C” in tables and listings. - Display Page number. - In the case there is no qualified data for the listings, express ‘No data available’.

General Setting for Title and Footnote

Title1	GTI 1401	Page 1 of x
Title2	<x title of section>	
Title3	<x x title of sub section or title of table, listing and figure>	
Title4	<x x x title of table, listing and figure>	
Title5	<target populaton>	
	column1	column2
	column3	column4
	column5	column6
	column7	
Footnote 1	table footnotes (if necessary)	
 
In this Layout Plan, only the table footnotes will be presented in each sheet. > For GTI1401-OLE, title 1 will be changed to "GTI1401-OLE"
 

....	table footnotes (if necessary)	
Footnote n	table footnotes (if necessary)	
Footnote n+1	table footnotes (if necessary)	
Footnote n+2	table footnotes (if necessary)	

GTI 1401
6 Subject Disposition
6.1 Summary Table of Analysis Population

All subjects screened

Population	n (%)
All subjects screened	xx
Safety population	xx
PK population	xx (xx x)

* Denominator of tabulation is the number of Safety Population

GTI 1401

6 Subject Disposition

6.2 Summary Table of Subjects Who Discontinue From the Study

Safety population

	N=88
Reason of Study Discontinuation	n (%)
Subjects who complete the study	xx (xx x)
Subjects who discontinue from the study	xx (xx x)
Adverse Event	xx (xx x)
Withdrawal By Subject (Does not Include AEs)	xx (xx x)
••••	xx (xx x)

* Denominator of tabulation is the number of Safety Population

GTI 1401
 6 Subject Disposition
 6.3 Listing of Subject Disposition

All subjects screened

Subject Number	Safety/ PK Population	Date of Screening /Date of Last Visit (Study Day)	Complete Study	Reason for Early Discontinuation	Reason for Exclusion of Safety Population	Reason for Exclusion of PK Population
xxx	Y/N	yyyy-mm-dd / yyyy-mm-dd	N	OTHER: xxx		xxx
xxx	Y/Y	yyyy-mm-dd / yyyy-mm-dd	Y			
xxx						

>Listing for "Screening Failures" will be also provided in same format.
 >Row 6 Column 3 will be changed to "Screening Failures".

>Sort order;
 Subject Number

>Date of last date for who completes study is date of completion of disposition event.
 Date of last date for who discontinues is date of discontinuation of disposition event.

GTI 1401
 7 Protocol Deviations
